10.6.2.2 Handling of Partial Dates

Element	Reporting Detail
Concomitant Medications	
 • Partial dates for any concomitant medications recorded in the CRF will be imputed using the following convention: 
 • If the partial date is a start date, a '01' will be used for the day and 'Jan' will be used for the month • If the partial date is a stop date, a '28/29/30/31' will be used for the day (dependent on the month and year) and 'Dec' will be used for the month. • The recorded partial date will be displayed in listings.
Adverse Events	
 • Any partial dates for adverse events will be raised to data management. If the full date cannot be ascertained, the following assumptions will be made for calculating the time to onset and the duration of the event: 
 • If the partial date is a start date, a '01' will be used for the day and 'Jan' will be used for the month, unless this is before the start date of investigational product; in this case the study treatment start date will be used (and hence the event is considered on-treatment as per Appendix 3: Treatment States). • If the partial date is a stop date, a '28/29/30/31' will be used for the day (dependent on the month and year) and 'Dec' will be used for the month, unless this is after the stop date of study treatment; in this case the study treatment stop date will be used. • The recorded partial date will be displayed in listings.

10.6.2.3 Handling of PK Concentration Data

Element	Reporting Detail
General	
 The PK Population will include all subjects who undergo PK sampling and have evaluable PK assay results. This population will be used for the concentration listing, summaries and plotting of the individual concentration-time profiles. PK assay results from samples collected from a subject with vomiting occurring within 2 times the median Tmax will not be considered as evaluable for that period. If the pre-dose concentration is $\leq 5\%$ of Cmax value in a subject, the concentration data for that subject without any adjustments will be included in pharmacokinetic and statistical analysis. If the pre-dose concentration is $> 5\%$ of Cmax value in a subject, then the concentration data for that subject will not be included in pharmacokinetic and statistical analysis and only the concentration data of that subject(s) will be presented For missing and NQ values, refer to GUI_51487.

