4. STUDY DESIGN

4.1. Part A (Single Dose)

Figure 1 Part A Schematic

★ Dose escalation meeting

- o One of the dosing periods will be a food effect group – the dose will be determined based on data from previous cohorts
- o There will be a 2 week washout between doses initially but the washout period may be modified depending on emerging data from previous cohorts.
- o Cohorts 1 and 2 will be dosed sequentially. If it is considered desirable to dose Cohorts 1 and 2 in an overlapping/interlocking fashion, approval will be sought from the Regulatory Agency first.

Up to two cohorts will be included in the single dose part (Part A). Each cohort will participate in up to 4 treatment (dosing) periods (including a food effect treatment period). Initially, there will be a 14 day wash out period for individual subjects between each dose level which is considered sufficient in light of the predicted half-life of GSK3036656 [on average, approximately 30 hours (range: 12 to 72 hours) based on the various preclinical extrapolation methods], however this may be revised once relevant PK data is obtained. Nine subjects per cohort will be enrolled and randomised to ensure adequate safety, tolerability and PK information is gained and a balanced randomisation is achieved across all treatment (dosing) periods.

During each treatment (dosing) period, GSK3036656 will be administered to 6 subjects and placebo will be administered to 3 subjects. As this is a FTIH study, each treatment (dosing) period will be staggered over 2 days. On Day 1 of each dose level, one subject will receive GSK3036656 and one subject will receive placebo. The remaining subjects within the dosing group will be dosed one day later provided satisfactory safety and tolerability is demonstrated for the subjects dosed on Day 1. A treatment (dosing) period does not have to be staggered if the dose administered is equal to or lower than a dose that has been already tested and found to be safe and well tolerated.

Subjects will attend the unit on Day -1 for assessments and a meal. The subjects will then fast overnight (at least 8 hours) and be dosed the following morning (Day 1). Dosing with food may also be done in Part A once results from the food effect analysis are available. Dividing the total dose for the treatment (dosing) period into 2 or 3 smaller doses administered within 24 hours may also be done. The decision to divide the total dose into

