5. Blood pressure, heart rate, tympanic temperature and respiratory rate. Vital signs will be recorded: at pre-dose and at 0.5, 1, 2, 3, 4, 6, 12, 24, 48 and 72 h after dosing on Days 1 and 14; and at pre-dose on Days 5-13.
6. ECGs will be recorded at pre-dose and at 0.5, 1, 2, 3, 4, 6, 12, 24, 48 and 72 h after dosing on Days 1 and 14; and at pre-dose on Days 6 and 10. Triplicate measurements (about 2-5 mins apart) will be taken at pre-dose; single measurements will be taken at all other time points.
7. 24 h Holter monitoring at screening only.
8. Telemetry will be recorded from -1 h pre-dose until 24 h post-dose on Day 1.
9. Haematology, clinical chemistry and urinalysis will be done on Day-1 and in the morning (pre-dose if feasible) on Days, 4, 6, 10, and 15.
10. Pregnancy testing of female subjects only. At screening pregnancy test will be done using the blood sample; urine pregnancy test will be done on Day-1.
11. Blood samples for assay of GSK3036656 will be taken: at pre-dose and at 0.25, 0.5, 0.75, 1, 1.5, 2, 3, 4, 6, 8, 12, 15, 24, 36, 48 and 72 h after dosing on Day 1; and at pre-dose and at 0.25, 0.5, 0.75, 1, 1.5, 2, 3, 4, 6, 8, 12, 15, 24, 36, 48 and 72 h after dosing on Day 14. PK samples will also be taken pre-dose on Days 12 and 13.
12. Total urine collections for GSK3036656 will be performed at the following time points: pre-dose and 0-6, 6-12 and 12-24 h after dosing on Days 1 and 14.
13. AEs and concomitant medications will be recorded collected from the start of informed consent until the follow-up contact.

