7.2.1.3. Pharmacokinetic Parameters

7.2.1.3.1. Deriving Pharmacokinetic Parameters

- Refer to [Appendix 4](#): Data Display Standards & Handling Conventions (Section 10.4.3. Reporting Process & Standards).
- Plasma GSK3036656 concentration-time data will be analyzed by non-compartmental methods according to current working practices with WinNonlin 5.2 or higher.
- Non-compartmental analysis will be performed in accordance with GSK PK Guidance document GUI_51487.
- All calculations of non-compartmental parameters will be based on actual sampling times recorded during the study.
- Pharmacokinetic parameters described in [Table 5](#) will be determined from plasma concentration-time data and urine concentration data, as data permits.

Table 5 Derived Pharmacokinetic Parameters

Parameter	Parameter Description
AUC(0-t)	Area under the concentration-time curve from time zero to the time of the last quantifiable concentration (C(t)) will be calculated using the linear trapezoidal rule for each incremental trapezoid and the log trapezoidal rule for each decremental trapezoid.
AUC(0-∞)	Area under the concentration-time curve extrapolated to infinity calculated as: $\text{AUC} = \text{AUC}(0-t) + C(t) / \lambda_z$
AUC(0-24h)	Area under the concentration-time curve from time zero to 24 hours post-dose
AUC(0-τ)	AUC from time zero during a dosing interval of duration “τ”
AUC(Ro)	Observed accumulation ratio (Ro) for AUC will be calculated as follows: $\text{Day 14 AUC}(0-\tau) / \text{Day 1 AUC}(0-\tau)$
Ae	Urinary excretion of unchanged drug
Cmax	Maximum observed blood concentration, determined directly from the concentration-time data.

Parameter	Parameter Description
Ctrough	Pre-dose observed concentration, will be obtained directly from the concentration-time data.
CLr	Renal clearance
Fe	Fraction of the dose excreted in the urine
Lambda_z	The first order rate constant associated with the terminal (log-linear) portion of the concentration-time curve.
Rss	Steady state ratio (Rss) will be calculated as follows: Day 14 AUC(0- τ)/Day 1 AUC(0- ∞)
RCmax	Observed accumulation ratio for Cmax (RCmax) will be calculated as follows: Day 14 Cmax/Day 1 Cmax
tmax	Time to reach Cmax, determined directly from the concentration-time data.
t _{1/2}	Apparent terminal phase half-life will be calculated as: $t_{1/2} = \ln 2 / \text{Lambda}_z$ (NOTE: Lambda_z is the terminal phase rate constant).

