
 Point estimates and 90% confidence intervals for the differences “Day 14- Day 1” will be constructed using the appropriate error term. The point estimates and associated 90% confidence intervals will then be exponentially back-transformed to provide point and 90% confidence interval estimates for the ratios “Day 14: Day 1” for each active dose. If both the dose and day by dose interaction terms are not significant, a single point estimate and confidence interval pooled across all doses will also be constructed.
--

Pharmacokinetic Statistical Analyses (Achievement of Steady State - Repeat Dose Study Phase)

Endpoint(s)

• Trough plasma concentrations at the end of the dosing interval (C _T)
--

Model Specification

 Will be statistically analysed using a mixed models (MM) using log-transformed dose data. Fixed effects : dose, day and dose*day Random Effect : Subject

 The Kenward and Roger method for approximating the denominator degrees of freedom and correcting for bias in the estimated variance-covariance of the fixed

Pharmacokinetic Statistical Analyses (Achievement of Steady State - Repeat Dose Study Phase)

effects will be used.

- An unstructured covariance structure for the G matrix will be used.
 - In the event that this model fails to converge, alternative covariance structures may be considered such as VC or CS.
 - Akaike's Information Criteria (AIC) will be used to assist with the selection of covariance structure.

Model Checking & Diagnostics

- Refer to [Appendix 8: Model Checking and Diagnostics for Statistical Analyses](#).

Model Results Presentation

The coefficients of the slopes for the day effect for each dose, along with corresponding 90% confidence intervals, will be used to determine whether steady state was achieved. If the day-by-dose interaction were not significant, then the point estimates and 95% CIs for the individual dose levels will also be pooled across all doses for a single D14/D1 ratio.

Trough concentration levels collected pre-morning dose will be plotted by collection day and dose.

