10.1 Appendix 1: Protocol Deviation Management

There are no pre-defined categories leading to exclusion from the PK population but all protocol deviations will be reviewed on a case-by-case basis.

No subjects will be excluded from the safety population.

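### The SAP's exclusion for pre-dose values above 5% of Cmax is not limited to drug-free profiles and, as written, removes nearly all Day 14 data in Part B

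*SAP*

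**What the plan says.** SAP 10.6.2.3, under its general heading for PK concentration data, keeps a subject's data unadjusted when the pre-dose value is at or below 5% of Cmax. Otherwise: "If the pre-dose concentration is $> 5\%$ of Cmax value in a subject, then the concentration data for that subject will not be included" in the pharmacokinetic and statistical analysis, and "only the concentration data of that subject(s) will be presented". The rule names no study part, day or dose. It does not say which pre-dose sample or which Cmax is meant. The vomiting rule in the same list, by contrast, is limited to the affected period.

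The documents use the same term for samples taken during repeat dosing:

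- Protocol 7.1, Table 2, footnote 11: "PK samples will also be taken pre-dose on Days 12 and 13", in addition to a pre-dose sample on Day 14.
- SAP Table 5 on Ctrough: "Pre-dose observed concentration, will be obtained directly from the concentration-time data".

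The SAP also plans analyses that need these data. Table 5 has "Observed accumulation ratio for Cmax (RCmax) will be calculated as follows: Day 14 Cmax/Day 1 Cmax", with Ro and Rss likewise built on Day 14 AUC. SAP 7.2.1.3.2 models trough concentrations over days, and the slopes "will be used to determine whether steady state was achieved". Repeat-dose proportionality uses AUC(0-τ) and Cmax.

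**The concern.** A pre-dose value above 5% of Cmax signals carry-over when the sample should be drug-free. During daily dosing it is the expected trough, and Protocol 6.3.2 itself expects exposure to be highest on the last dosing day because of accumulation. A rule that treats the trough as contamination conflicts with the analyses that the same SAP specifies.

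Two readings of the unit of exclusion are open. Read per subject, as the words stand, a high Day 14 pre-dose value removes all of that subject's Part B profiles, including Day 1. Read per profile, Day 1 survives and Day 14 does not. Either way Ro, RCmax, Rss, the time-invariance model and repeat-dose proportionality lose their Day 14 data, and the trough model loses the samples that it is fitted to. Any subjects who pass would be those with the fastest elimination, so the remaining sample would be selected on clearance. The alternative is that the analyst decides during reporting to depart from a pre-specified exclusion rule, which is the kind of choice that a SAP is meant to remove.

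**Working it through.** The plan gives no figure to reproduce, so the check asks how often the rule would be triggered on Day 14.

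**Inputs from the documents**

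- Half-life about 30 h on average, range 12 to 72 h (Protocol 4.1).
- Once-daily dosing for up to 14 days; 8 active subjects in each of up to 4 cohorts, so at most 8 × 4 = 32 (Protocol 4.2).
- 50% CV for clearance (Protocol 4.5).

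**Assumptions, because the documents do not give them**

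- One-compartment kinetics.
- Absorption rate ka from 0.5 to 3 per hour, or bolus input.
- Lognormal clearance with volume fixed, so half-life has log SD √ln(1 + 0.5²) = 0.472.

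**Step 1: Day 14 pre-dose value over Day 14 Cmax.** For bolus input, let b = 0.5^(24/t½). Thirteen doses precede the Day 14 sample and Cmax follows the fourteenth, so the ratio is b(1 − b¹³)/(1 − b¹⁴).

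- t½ 12 h: b = 0.250, ratio 0.250.
- t½ 30 h: b = 0.574, ratio 0.574.
- t½ 72 h: b = 0.794, ratio 0.785.

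For oral input, the same superposition is applied to the first-order absorption curve:

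| t½ | ka 0.5 | ka 1 | ka 2 | ka 3 | bolus |
|---|---|---|---|---|---|
| 12 h | 36% | 31% | 28% | 27% | 25% |
| 30 h | 67% | 63% | 61% | 60% | 57% |
| 72 h | 84% | 82% | 80% | 80% | 79% |

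The lowest entry is five times the 5% limit.

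**Step 2: half-life at which the ratio is exactly 5%.** For bolus input it is 24 × ln 2/ln 20 = 5.55 h. For ka 0.5, 1, 2 and 3 it is 4.24, 4.79, 5.10 and 5.23 h. All lie well below the stated range.

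**Step 3: expected number flagged of 32.** This is 32 × Φ[ln(median t½ / break-even t½)/0.472]. For bolus input at a median of 12 h: 32 × Φ[ln(12/5.55)/0.472] = 32 × Φ(1.63) = 30.4.

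| Median t½ | ka 0.5 | ka 1 | ka 2 | ka 3 | bolus |
|---|---|---|---|---|---|
| 12 h | 31.6 | 31.2 | 30.9 | 30.7 | 30.4 |
| 30 h | 32.0 | 32.0 | 32.0 | 32.0 | 32.0 |
| 72 h | 32.0 | 32.0 | 32.0 | 32.0 | 32.0 |

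**Step 4: sensitivity**

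- Pairing the PBPK clearance (7.2 mL/min/kg) and volume (3.5 L/kg) from Protocol 4.5 gives t½ = ln 2 × 3.5/(7.2 × 60/1000) = 5.6 h, outside the stated range. About 16 to 23 of 32 are still flagged.
- With a distribution phase, the trough falls below 5% of Cmax only if the distribution coefficient exceeds about 5.3 times the terminal one at 12 h, or about 25 times at 30 h. The documents do not suggest this.
- Divided daily doses, which the protocol allows, raise the ratio: the bolus break-even half-life drops to 2.8 h for 12-hourly and 1.9 h for 8-hourly dosing.

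**The case against.** The strongest reply is that the rule is obviously a carry-over check. The SAP specifies Ro, RCmax, Rss and trough analyses in detail, with tables and shells, so a reading that cancels all of them is the least plausible. The SAP's baseline section uses pre-dose for the Day 1 sample, so the rule may mean the sample before a subject's first dose. GUI_51487, which governs the non-compartmental analysis, may deal with steady-state profiles. Sampling is unaffected, flagged concentrations are still presented, and no formal hypothesis is tested, so nothing is lost for good.

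Part of this stands. Carry-over control is very probably the intent, and the underlying data would still exist. The rest does not settle the matter:

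- Read as the sample before the first dose ever, the rule is empty, because an undosed subject has no drug to measure. Read as Day 1 of each period, it is sensible, but that limit is what the text lacks.
- The baseline section does not govern PK exclusions, and elsewhere the documents apply pre-dose to Days 12 to 14.
- GUI_51487 cannot be consulted here. Section 10.6.2.3 invokes it only for missing and non-quantifiable values, and no SAP text says that it overrides the 5% rule.
- SAP Appendix 1 states "There are no pre-defined categories leading to exclusion from the PK population", with deviations reviewed case by case. That concerns membership of the population and neither limits nor extends a rule on concentration data.

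Moving the unit of exclusion from subject to profile also changes Part A, as the objection notes. There the present text leaves open whether one flagged period removes a subject's other periods, so this needs stating in any case.

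**Conclusion.** The concern holds. Followed as written, the rule excludes about 30 to 32 of at most 32 active Part B subjects from the Day 14 analyses across the protocol's stated half-life range. The count rests on one-compartment kinetics, an assumed absorption rate, fixed volume and all four cohorts being run. The conclusion does not depend on the absorption rate: every ratio in the stated range is at least five times the limit. It weakens only at half-lives near 5.6 h, where roughly half or more are still flagged. Because the text defeats planned analyses that serve a primary objective, it must be corrected before the database is frozen and not left to interpretation.

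**What to change.** Amend SAP 10.6.2.3 as follows:

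1. Apply the 5% rule only to profiles whose pre-dose sample should be drug-free: each Part A period and Part B Day 1.
2. State that it does not apply to pre-dose samples on later Part B days, where the value is a trough and is analysed as such.
3. Exclude the affected profile, not all of the subject's data.
4. State that the pre-dose value and Cmax are taken from that same profile.

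Under this wording the rule excludes no Day 14 profile. The cost is a short change to SAP text. Sampling, sample size and the planned models are unchanged.

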7.3. Pharmacokinetics

7.3.1. Blood Sample Collection

Blood samples for plasma PK analysis of GSK3036656 will be collected into K3 EDTA tubes at the time points indicated in the Time and Events Table (Section [7.1](#)). The actual date and time of each blood sample collection will be recorded. In the repeat dose part of the study on days 12 and 13, PK samples will be taken pre-dose to assess the achievement of steady-state of GSK3036656 following repeat oral doses. On the last dosing day of the repeat dose, subjects will undergo the same assessments as on Day 1. Subjects may then be discharged but will be required to return for the 36, 48 and 72 hour PK sampling. PK samples obtained on pre-dose and 24 hours post-dose on day 14 will also be used as part of the assessment to see if steady-state has been achieved.

The timing of PK samples may be altered and/or PK samples may be obtained at additional time points to ensure thorough PK monitoring.

Details of PK blood sample collection (including volume to be collected), processing, storage and shipping procedures are provided in the SRM.

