7.1.1. Overview of Planned Bayesian Dose Escalation Analyses

The Bayesian Dose Escalation analyses will be utilised to guide dose selection after 3 doses in each part of the study. The analyses will be based on the PK population, unless otherwise specified.

During dose escalation, a Bayesian predictive probability of geometric mean $AUC[0-24] > 4.9 \mu\text{g.h/ml}$ and $C_{max} > 0.443 \mu\text{g/ml}$ will be calculated for potential future dose levels and used together with safety and tolerability data to aid next dose selections. The Bayesian predictive probability will be based on Whitehead's method (Whitehead 2001).

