7.2.1.3.2. Statistical Analysis of Pharmacokinetic Parameters

For each of the parameters AUC (AUC(0- ∞), AUC (0- t), AUC(0- τ), AUC(Ro)), RCmax, Rss, Ct, Ae, fe, CLr and Cmax the following summary statistics will be calculated and tabulated by dose group for study Part A and Part B separately:

- **Untransformed Data:** N, n, arithmetic mean, 95% confidence interval (CI) for the arithmetic mean, SD, median, minimum, maximum.
- **Log_e-transformed Data:** Geometric mean, 95% CI for the geometric mean, SD of log_e-transformed data and %CVb.

For tmax, and t_{1/2} the summary statistics specified for untransformed data above will be generated.

The following pharmacokinetic statistical analyses will only be performed, if sufficient data is available (i.e. if subjects have well defined plasma profiles). Pharmacokinetic analysis will be the responsibility of the Clinical Pharmacology Modeling and Simulation Department, (CPMS) and Statistical analyses of the pharmacokinetic parameter data will be the responsibility of QSI Stats & Programming.

Pharmacokinetic Statistical Analyses (Dose Proportionality - Single and Repeat Dose Study Phases)	
Endpoint(s)	

 • Single Dose: AUC(0-t), AUC(0-∞) and Cmax • Repeat Dose : AUC(0-τ) and Cmax 	
Model Specification	

 • Will be statistically analysed using the power model • $y = \alpha^* \text{dose}^\beta$ 
Where y =PK parameter being analyzed and α= subject
 
 • Log_e transformed data will be analysed by fitting the following terms in the mixed effect model: 
 • Fixed effect: log_e (dose) • Random effect: Subject 	
Model Checking & Diagnostics	

 • Refer to Appendix 8: Model Checking and Diagnostics for Statistical Analyses. 	
Model Results Presentation	
Estimates of the mean slopes of log _e (dose) will be reported along with corresponding 90% confidence intervals (slope≈1 implies dose proportionality).	

Pharmacokinetic Statistical Analyses (Food Effect - Single Dose Study Phase)	
Endpoint(s)	

 • AUC(0-t), AUC(0-∞), Cmax and t_{1/2} 	
Model Specification	

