
 • Will be statistically analysed using a mixed model (MM) ANOVA. • Fixed, categorical effect : day • Random Effect : Subject 
AUC(0-inf) on Day 1 will be the reference phase in the analysis, while AUC(0- τ) on Day 14 will be the test phase, using log-transformed AUC.
	

 • The Kenward and Roger method for approximating the denominator degrees of freedom and correcting for bias in the estimated variance-covariance of the fixed effects will be used. • An unstructured covariance structure for the G matrix will be used. 
 ◦ In the event that this model fails to converge, alternative covariance structures may be considered such as VC or CS. ◦ Akaike's Information Criteria (AIC) will be used to assist with the selection of covariance structure. 	
Model Checking & Diagnostics	

 • Refer to Appendix 8: Model Checking and Diagnostics for Statistical Analyses. 	
Model Results Presentation	

 • The time invariance ratio of GSK3036656 will be estimated by calculating the ratio of the generalized least square means of AUC (0- τ) on Day 14 to AUC (0-inf) on 	

Pharmacokinetic Statistical Analyses (Time Invariance of GSK3036656 - Repeat Dose Study Phase)

Day 1, along with the corresponding 90% CI at each dose level.
--

Pharmacokinetic Statistical Analyses (Accumulation - Repeat Dose Study Phase)
--

Endpoint(s)

• AUC (Ro) and Cmax (RCmax)

Model Specification

 Will be statistically analysed using a mixed model (MM) using a log_e-transformation. Fixed effects : dose, day and dose*day Random Effect : Subject

 The Kenward and Roger method for approximating the denominator degrees of freedom and correcting for bias in the estimated variance-covariance of the fixed effects will be used. An unstructured covariance structure for the G matrix will be used. 
 In the event that this model fails to converge, alternative covariance structures may be considered such as VC or CS. Akaike's Information Criteria (AIC) will be used to assist with the selection of covariance structure.

Model Checking & Diagnostics

• Refer to Appendix 8 : Model Checking and Diagnostics for Statistical Analyses.
--

Model Results Presentation

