10.6.2 Handling of Missing Data

Element	Reporting Detail
General	
 Missing data occurs when any requested data is not provided, leading to blank fields on the collection instrument : 
 These data will be indicated by the use of a “blank” in subject listing displays. Unless all data for a specific visit are missing in which case the data is excluded from the table. Answers such as “Not applicable” and “Not evaluable” are not considered to be missing data and should be displayed as such.
Outliers	
 Any subjects excluded from the summaries and/or statistical analyses will be documented along with the reason for exclusion in the clinical study report.

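### The 5% pre-dose exclusion in SAP 10.6.2.3 is not limited to single-dose carryover, so as written it removes most or nearly all Part B Day 14 profiles

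*SAP*

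**What the plan says.** SAP 10.6.2.3 gives two paired rules under a General heading. If pre-dose is at or below 5% of Cmax, the subject's data enter the analysis unadjusted. If it is above 5%, "then the concentration data for that subject will not be included in pharmacokinetic and statistical analysis", and the concentrations are only presented. No study part, day or period is named. The vomiting rule in the same cell is limited: affected results "will not be considered as evaluable for that period".

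The SAP uses the same term for on-treatment troughs. Table 5 (SAP 7.2.1.3.1) defines Ctrough as the pre-dose concentration, and the Part B schedule takes pre-dose samples on Days 1, 12, 13 and 14.

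SAP 7.2.1.3.2 then plans analyses that need Day 14 data:

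- Accumulation compares Day 14 with Day 1 AUC(0-τ) and Cmax.
- Time invariance tests Day 14 AUC(0-τ) against Day 1: "AUC(0-inf) on Day 1 will be the reference phase in the analysis".
- Repeat-dose proportionality uses AUC(0-τ) and Cmax.
- For steady state, slopes of trough on day "will be used to determine whether steady state was achieved". Protocol 7.3.1 adds that "PK samples obtained on pre-dose and 24 hours post-dose on day 14 will also be used as part of the assessment".

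Nothing in SAP Section 4, Appendix 1 or 10.5.4 narrows the 5% rule. The internal guidance GUI_51487 is cited in 10.6.2.3 for missing and non-quantifiable values, and in 7.2.1.3.1 for non-compartmental analysis in general. Its content is not available here.

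**The concern.** A pre-dose level above 5% of Cmax signals unwanted carryover only when the previous dose should have washed out. Under daily dosing of a drug with a half-life near or above the dosing interval, a substantial trough is expected, and it is part of what Part B sets out to measure. A rule with no limit to single-dose periods therefore excludes the very profiles that the repeat-dose analyses require.

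Reading the rule profile by profile does not remove the conflict, because the Day 14 profile fails the test by itself. Reading it subject by subject is worse: the subject's Day 1 profile and the Day 12 and 13 troughs would go too.

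The analyst must then either lose the planned Day 14 analyses or set aside a written rule without text that authorises it. In Part A, the subject-level wording could also cost valid within-subject data from a small crossover.

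**Working it through.** The plan gives no figure of its own on this point, so there is nothing to reproduce. The check asks how a Day 14 trough compares with 5% of Cmax.

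**Inputs.** Half-life about 30 h, range 12 to 72 h (Protocol 4.1). Daily dosing for up to 14 days, 8 active subjects in each of up to 4 cohorts (Protocol 4.2), so up to 8 × 4 = 32 Day 14 profiles. The 50% CV is the protocol's simulation value for clearance (4.5), applied here to half-life; a 30% CV is shown as an alternative assumption. Half-life is taken as log-normal.

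**Step 1: expected ratio.** Let r = 2^(−24/t½), and let f be the share of a dose's peak that belongs to the terminal phase (f = 1 is one compartment with rapid absorption). Thirteen earlier doses give a trough P = f × (r + r² + … + r¹³) in units of one dose's peak. The ratio is P/(P + 1).

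At 30 h and f = 1: r = 2^(−0.8) = 0.574, P = 1.348, ratio = 1.348/2.348 = 0.574.

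| Half-life | f = 1 | f = 0.5 | f = 0.2 |
|---|---|---|---|
| 12 h | 25% | 14% | 6% |
| 30 h | 57% | 40% | 21% |
| 72 h | 79% | 65% | 42% |

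Slower oral absorption raises the one-compartment figures. With absorption rate constants of 0.3 to 5 per hour the ranges are 27–43%, 59–72% and 79–86%. Divided daily dosing, which the protocol allows, shortens the interval and would raise them further.

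**Step 2: half-life at which the rule starts to exclude.** The ratio exceeds 0.05 when P > 1/19. After 13 doses at these short half-lives P is close to f × r/(1 − r), so:

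- f = 1: r = 1/20, t½ = 24/log₂(20) = 5.6 h
- f = 0.5: r = 2/21, t½ = 24/log₂(10.5) = 7.1 h
- f = 0.2: r = 5/24, t½ = 24/log₂(4.8) = 10.6 h

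All three lie below the protocol's range of 12 to 72 h.

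**Step 3: share of Day 14 profiles excluded.** Share = 1 − Φ(ln(t*/median)/s), where t* is the Step 2 value and s = √ln(1 + CV²), that is 0.294 at 30% CV and 0.472 at 50% CV.

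| Median half-life | f = 1 | f = 0.5 | f = 0.2 |
|---|---|---|---|
| 12 h, CV 30% / 50% | 99.6% / 95% | 96% / 87% | 66% / 60% |
| 30 h, CV 50% | 99.98% | 99.9% | 98.6% |

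Of 32 profiles, that runs from about 19 (0.60 × 32) in the least affected case shown to essentially all 32 at the predicted 30 h.

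**Step 4: Part A under the subject-level reading.** A full cohort has 6 × 4 = 24 active profiles and 3 × 4 = 12 placebo slots over 9 subjects. If placebo rotates as evenly as possible, six subjects have 3 active profiles and three have 2 (6 × 3 + 3 × 2 = 24). One carryover flag would then cost 2 or 3 profiles where 1 is affected. Flags should be rare: the planned 14-day washout leaves 2^(−336/30) = 0.04% at 30 h and 2^(−336/72) = 3.9% at 72 h, at equal dose.

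**The case against.** The strongest reply is that no one would apply the rule this way. The SAP explicitly defines and analyses Day 14 quantities, so a general carryover bullet cannot be meant to cancel them. The conflict is visible from the design before any data exist, so resolving it need not be driven by results. Exclusions would be traceable: "Any subjects excluded from the summaries and/or statistical analyses will be documented along with the reason for exclusion". All of this is fair, and the intent was probably a single-dose rule. But the text says otherwise, and a rule that contradicts the analyses beside it should be corrected rather than left to each analyst.

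The paired bullets also count against the subject-level reading. A subject with one period on each side of 5% would be both included and excluded, so the rule works consistently only per profile. That makes the Part A point an ambiguity. It does not rescue Part B. Read per profile, the Day 12 and 13 troughs survive, since no Cmax is measured on those days, so only part of the steady-state analysis is affected.

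The size depends on the half-life. One extreme pair in Protocol 4.5 (clearance 7.2 mL/min/kg, volume 3.5 L/kg) gives ln 2 × 3500/(7.2 × 60) = 5.6 h and a ratio of about 5.2%, right at the limit. The protocol's own stated range nevertheless starts at 12 h.

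A reader might infer that dose-escalation safety is compromised, because SAP 7.1.1 says "The analyses will be based on the PK population, unless otherwise specified" and the exclusion covers statistical analysis generally. The documents do not support that. The stopping criterion in Protocol 5.5 acts on any subject's AUC(0-24) or Cmax, and the Dose Escalation Committee reviews all available PK data.

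**Conclusion.** The point holds as a drafting error with real consequences if followed literally. The rule, as written, excludes most or nearly all Part B Day 14 profiles. At the predicted 30 h half-life at least 98% fail the 5% test even if only a fifth of Cmax is terminal phase. At a 12 h median the share is 60% to 99.6%, depending on f and CV. These figures rest on first-order elimination, the protocol's half-life range, log-normal half-life and the assumed CVs. The conclusion that typical troughs exceed 5% holds across the stated range under every f shown. The Part A reading is possible but not certain, and few subjects should be affected.

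Two stronger inferences are not supported. A reader might conclude that the protocol's minimum washout of 4 half-lives (2^(−4) = 6.25% left at equal dose) clashes with the 5% limit and needs an amendment. A dosing floor and an analysis threshold need not coincide, and the planned 14 days leaves 3.9% even at 72 h and equal dose. A reader might also infer a material bias in AUC(0-∞), or a breach of an extrapolation limit. The SAP states no such limit, asking only for well-defined plasma profiles.

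**What to change.** Reword SAP 10.6.2.3 so that:

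- in Part A, a pre-dose concentration above 5% of Cmax excludes only the affected period's profile;
- in Part B, the rule applies only to the Day 1 pre-dose sample;
- it expressly does not apply to later Part B pre-dose samples (Days 12, 13 and 14).

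This is one or two lines of SAP text, with no extra subjects, samples or visits and no protocol amendment. It is best settled before any Part B Day 14 data are analysed.

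Two optional additions: state that observed values stay in the dose-escalation dataset whatever is excluded from the final analysis (one line), and report the results with and without any excluded Part A profile (one conditional rerun).
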